1.4 Background and rationale of correlative studies

1.4.1 DNMT1 expression

The intended molecular target of decitabine therapy is the key epigenetic regulator DNMT1. In order to deplete DNMT1, decitabine, a pro-drug, is processed via pyrimidine metabolism into a nucleotide Aza-dCTP that incorporates into the newly synthesized DNA strand during cellular S-phase. Natural deoxycytidine (dCTP) directly competes with Aza-dCTP for incorporation into DNA, and accordingly, a major mechanism by which malignant cells evade DNMT1-depletion by decitabine is by upregulating de novo pyrimidine synthesis that synthesizes dCTP from glutamine and aspartate building blocks. We hypothesize that a single dose of venetoclax once a week prior to subcutaneous decitabine the next day counters this mechanism of resistance by temporarily inhibiting de novo pyrimidine synthesis, that requires intact mitochondrial membrane potential. Thus, the key correlative study in this study is measurement of DNMT1 levels in the bone marrow. By confirming the ability of to maintain DNMT1 depletion in a clinical setting, this study aims to be foundational in future studies by demonstrating appropriate testing intervals for biological correlates. Moreover, monitoring the DNMT1 repletion over time along with at the time of progression or relapse will indicate mechanisms of resistance to this therapeutic strategy. In other words, whether relapse was specifically associated with a failure to maintain DNMT1 depletion or another mechanism. DNMT1 protein levels will be measured in bone marrow biopsy specimens using immunohistochemistry (IHC), complemented by flow cytometry analysis of peripheral blood white cells that are in G1. The correlatives will be done at the Cleveland clinic laboratory of [name].

1.4 Rationale for cohort expansion (ammendment):

- In a retrospective cohort of patients treated at Montefiore-Einstein with this regimen of weekly low dose decitabine/venetoclax (LDDec/VEN) we compared the experience with the low dose regimen to a cohort of contemporaneous patients treated with standard dosing HMA/VEN per the VIALE-A trial (Levitz et al CCR in press) . The ORR for frontline AML and MDS patients for LDDec/VEN was 88% and 64% respectively, similar to the standard dosing regimen. Importantly, we showed that the LDDec/VEN cohort had a much longer time on therapy when compared to patients who received standard VIALE-A dosing (175 vs 78 days; p= 0.014) and a numerical trend toward a higher rate of transfusion independence (53% vs 26%), although this did not reach statistical significance (p=0.33). A preliminary analysis of the data from the initial 17 evaluable patients **enrolled** in this protocol (patients who completed 12 week of induction), demonstrated that only one patient had a dose interruption during induction (one dose held) and no patients required dose reductions. The majority of these patients had AML (n=11) with an ORR of 64% (7/11) and 6/7 responses are ongoing. Given the early high tolerability of the low dose regimen (primary endpoint) and encouraging activity (secondary endpoint), combined with our reported in retrospective data referenced above, adding additional patients in selected subsets of patients will allow further confirmation of the safety and tolerability of this novel low dose metronomic regimen as well as to generate preliminary efficacy data (secondary endpoints) to guide sample size estimates for further clinical development. Data from these additional patients will also help in defining the safety and efficacy profile of this regimen to allow for rationale design of future combination trials using the low dose metronomic HMA/VEN backbone with additional agents to achieve further progress in clinical outcomes for patients with MDS and AML.

2.0 OBJECTIVES

2.1 Primary Objective

1. Percentage of MDS and AML participants who are able to continue on treatment without dose interruptions or delays, defined as delaying or interrupting treatment due to toxicity or intolerability for more than two weeks

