Rationale	
Noncytotoxic dosing of decitabine given weekly at a dose of 0.2 mg/kg induces depletion of DNA methyltransferase 1 (DNMT1) while minimizing the toxicity and myelosuppression seen with standard HMA dosing regimens. This approach has been shown to be effective in a wide spectrum of patients with myeloid malignancies, including patients with resistant disease such as P53 mutations.
 
Preclinical studies have demonstrated that adding a dose of venetoclax prior to administering decitabine enhances the anti-leukemic activity of HMAs by inhibiting de novo pyrimidine synthesis, which is a major mechanism of resistance to HMA in MDS/AML. Decreasing the dose of venetoclax to a weekly schedule also spares normal myelopoiesis. Therefore, a weekly dosing of decitabine/venetoclax is a very attractive option for a patient population who cannot tolerate or are not known to benefit standard Aza/ven.

Primary Objective	
Primary Endpoint
 
Percentage of participants who are able to continue on treatment without dose interruptions or delays. Defined as delaying or interrupting treatment due to toxicity or intolerance during the induction phase (weeks 1-12)

Secondary Objective(s)	
Secondary Endpoints: (1) Cumulative incidence of response for both CR, CRI and overall response; (2) Event free survival

	
(EFS); (3) Complete remission or complete remission with partial hematologic recovery rate (CR+CRh); (4) Post baseline transfusion dependence rate; (5) Fatigue/quality of life (QoL); (6) Rate of hospitalization; (7) Infection rate
 
Scientific Correlates:
 
Correlation of DNMT1 depletion with clinical response criteria

Sample Size	85 patients
Disease sites/Conditions	Myeloid malignancies: ≥MDS, AML, MDS/MPN overlap syndrome
• Interventions	
 • Venetoclax 400 mg po on days 1, 8, 15 and 28 of each cycle (28day cycle) (+/- 1 day allowed). • Decitabine 0.2 mg/kg SQ on days 1, 8, 15, 22 (for aggressive disease will add decitabine on days 2, 9, 16, 23)

TABLE OF CONTENTS

SUMMARY OF CHANGES	3
ABBREVIATIONS.....	5
STUDY SCHEMA	6
PROTOCOL SUMMARY	7
TABLE OF CONTENTS	9
1.0 INTRODUCTION	12
1.1 BACKGROUND.....	12
1.1.1 Diseases- Myeloid malignancies: Acute Myelogenous Leukemia (AML) and Myelodysplastic Syndromes (MDS) and Myeloproliferative neoplasms (MPN).....	12
1.1.2 Treatment of myeloid malignancies	12
1.2 STUDY RATIONALE.....	14

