3.1 Number of Subjects

In the initial safety and tolerability phase of the study, 33 patients will be enrolled on this study, accounting for need for replacement subjects to evaluate endpoints. In the second expansion phase of the study up to 85 patients (including patients from the 1st stage), will be enrolled to obtain additional safety, tolerability and preliminary efficacy of the low dose regimen in selected subsets of patients with myeloid malignancies.

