4.1 Inclusion Criteria

Subjects must meet all of the following inclusion criteria to be eligible for enrollment:

1. Patient must have a diagnosis of MDS, AML, CMML or MDS/MPN with a histopathologic diagnosis confirmed by hematopathology review

AND

2. Indication for therapy with potential sensitivity to HMA therapy, defined as prior published evidence of response to HMA.

AND

3. Patients must be 18 years of age or older

AND

4. Patients must have an ECOG performance status of ≤ 3

AND

5. Patients must have adequate end organ function defined as.

- AST and ALT $< 4 \times$ the upper limit of normal (ULN)
- Bilirubin $\leq 2 \times$ the ULN. If elevated bilirubin is due to impaired conjugation (e.g. Gilbert's disease or concomitant medication) or disease related hemolysis, then direct bilirubin $\leq 1.5 \times$ the ULN.
- As decitabine and venetoclax have little renal metabolism, and have proven safety even in dialysis patients, renal function with a creatinine clearance ≥ 30 mL/min or on dialysis is allowed.¹⁸

AND

6. Subjects must have the ability to understand and the willingness to sign a written informed consent document and complete study related procedures.

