Considerations in choice of primary end-point: The primary end-point is the overall percent of patients who can receive weekly low dose decitabine/ven during the induction period (weeks 1-12) without dose interruptions. The reason for the 12-week time period was used is because responses to HMA/ven are gradual and more so with the low dose regimen. For example, in VIALE-A, the median time to first response (either complete remission or complete remission with incomplete hematologic recovery) was 1.3 months (range, 0.6 to 9.9) and 2.8 months (range, 0.8 to 13.2), respectively.

Considerations in sample-size calculations: As mentioned above, in VIALE-A dose interruptions were required in 72% of patients receiving standard currently approved dosing of Aza/ven. Therefore, the sample size has been calculated to detect a 50% reduction in treatment interruptions, which would suggest that the proposed regimen has a high likelihood of being an advance over the current FDA approved regimen.

Sample size calculations: A Simon 2-stage Optimal design is used to test the null hypothesis of 60% or more patients requiring a dose reduction versus the alternative hypothesis of 36% or less of patients requiring dose interruptions with a one-sided alpha of 5%, power of 80%, and a probability of early termination of 0.77. After assessing dosing of decitabine/ven in 13 patients in the first stage, the trial will be terminated if 7 or more patients require dose reduction. If the trial goes on to the second stage, a total of 33 patients will be studied. If the total number of dose reduction is greater than or equal to 16, the treatment regimen is rejected.

After the 19 patients were enrolled into the study and 17 patients were evaluable after a 12-week induction, there were with no safety concerns. If after a total of 33 patients have been evaluated after the 12-week induction period and show satisfactory results (i.e., fewer than 16 dose reductions during the induction period, so the treatment was not rejected), the proposed amendment for an expansion phase will be implemented in which additional patients will be enrolled to gather more data on the secondary endpoints of efficacy using this regimen in MDS and AML. Background for the rationale for this amendment is outlined in section 1.4. Given the early efficacy seen in the first 11 evaluable patients with AML (64% response rate) and very low toxicity, more subjects will be required to establish the secondary

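### The plan names no single population for the primary two-stage test, and the 16-of-33 cut-off has its stated properties only if exactly 33 patients of one defined population are counted

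*Combined protocol and SAP*

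**What the plan says.** **Diagnoses.** Section 2.1 sets the primary objective as "Percentage of MDS and AML participants who are able to continue on treatment without dose interruptions or delays". The Protocol Summary has the same endpoint without the disease limit: "Percentage of participants who are able to continue on treatment without dose interruptions or delays". Section 13 also speaks of everyone: "The primary end-point is the overall percent of patients who can receive weekly low dose decitabine/ven during the induction period". Section 4.1 admits more than MDS and AML: "Patient must have a diagnosis of MDS, AML, CMML or MDS/MPN".

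**Which 33.** Section 3.1 says "33 patients will be enrolled on this study, accounting for need for replacement subjects to evaluate endpoints". Section 13 first describes 33 as the number studied, then opens the expansion phase on a different condition: "If after a total of 33 patients have been evaluated after the 12-week induction period", with fewer than 16 events.

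**Replacement.** Section 3.2 replaces patients who do not complete 12 weeks for reasons other than progression, and those who stop for toxicity. It keeps everyone who starts therapy evaluable for safety, but does not say whether a replaced patient stays in the primary test. Section 1.4 (rationale for cohort expansion) describes its 17 evaluable patients as those who finished the 12-week induction.

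**Decision rule.** Section 13 gives fixed counts: stop at 7 or more events among 13, and reject the regimen at 16 or more among 33. It gives no rule for any other denominator.

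**The concern.** This is the plan's only formal hypothesis test, and passing it opens the expansion phase. A cut-off written as a count works only for the denominator it was built on. If fewer patients are counted and 16 is kept, the test becomes easier to pass.

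The two counts of 33 also cannot both hold once anyone is replaced: 33 enrolled with replacements included yields fewer than 33 evaluated.

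The replacement rule raises a further problem. A patient who stops for toxicity during induction is a likely primary-endpoint event. If the test counts completers, that patient leaves the denominator and a patient who completes takes the place. The test then favours the regimen even when 33 are counted.

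**Working it through.** **Inputs, all from Section 13.** Null event rate 60%; alternative 36%; one-sided alpha 5%; power 80%; probability of early termination 0.77; first stage 13 patients, stop at 7 or more events; final stage 33 patients, reject at 16 or more. Here an event means whatever the test counts; the section uses both reduction and interruption, which is a separate matter.

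**Formula.** With event rate q and n patients finally counted, the regimen passes if there are at most 6 events in the first 13 and at most c in total:

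P(pass) = Σ over x = 0 to 6 of [C(13,x) q^x (1−q)^(13−x)] × P[Bin(n−13, q) ≤ c−x]

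Alpha is this value at q = 0.60 and power is its value at q = 0.36. The plan's rule is c = 15.

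**Step 1: reproduce the plan.** At n = 33, c = 15: alpha 0.0474, power 0.809, early termination under the null 0.771. A search for the optimal two-stage design with success rates 0.40 versus 0.64 returns the same cut-offs. The design is correct for 33 patients.

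**Step 2: vary the number counted.** The first stage stays at 13. The middle columns keep rejection at 16. The right-hand columns use the highest rejection count that holds alpha at or below 5%.

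| Counted | Alpha, 16 kept | Power, 16 kept | Recomputed: reject at | Alpha | Power |
|---|---|---|---|---|---|
| 33 | 0.0474 | 0.809 | 16 | 0.0474 | 0.809 |
| 32 | 0.0643 | 0.823 | 15 | 0.0361 | 0.784 |
| 31 | 0.0847 | 0.834 | 14 | 0.0265 | 0.748 |
| 30 | 0.1082 | 0.841 | 14 | 0.0384 | 0.776 |
| 29 | 0.1336 | 0.847 | 13 | 0.0278 | 0.735 |
| 28 | 0.1593 | 0.850 | 13 | 0.0408 | 0.766 |

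One patient fewer already exceeds 5%. Counting more than 33 has the opposite effect: at 38, alpha is 0.7% and power 68%.

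**Step 3: direction of the replacement effect.** Step 2 assumes that patients are left out independently of outcome. Suppose instead that a fraction d of treated patients stop for toxicity, that all of them are events, and that they are replaced by completers. At a true overall event rate of 0.60, the rate among those counted is (0.60 − d)/(1 − d). This is below 0.60 for every d > 0, because 0.60 − d < 0.60 − 0.60d. The chance of a false pass therefore rises above 4.7% even with 33 counted. The documents do not give d, so no size is attached.

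**The case against.** The strongest reply is that Section 13's own gate fixes the denominator. It opens the expansion only after 33 evaluated patients, and Section 3.2 supplies replacements, so 33 can be counted and the nominal alpha is 4.7%. Nothing in the plan applies 16 to 28–32 patients. This stands for exclusions unrelated to outcome. It does not answer the completer problem, and it does not remove the conflict with Sections 2.1 and 3.1.

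Three stronger readings are tempting, and the documents do not support them.

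- **That 29 or 30 of the 33 will be evaluable.** A reader might project 17 evaluable of 19 enrolled: 17/19 × 33 = 29.5. That figure is a snapshot. The other two may simply not have reached week 12; they are not described as drop-outs.
- **That several of the 33 have CMML or MDS/MPN and would drop out under Section 2.1.** No such count is given. Section 13's worked example divides the first 33 into 16 MDS and 17 AML and adds about 10 rare diagnoses on top (33 + 37 + 5 + 10 = 85). The example is illustrative, but it is the only accounting in the plan.
- **That the decision to expand is in doubt.** Section 1.4 reports 1 interruption and no reductions among 17 evaluable patients. Rejection would then need 15 events in the remaining 16 patients at n = 33, or 13 in 13 at n = 30 (recomputed cut-off 14). At n = 28 (cut-off 13) it would need 12 in 11, which is impossible. Scoring both other enrolled patients as events (3 of 19) still requires 13 of 14 at n = 33 and 11 of 11 at n = 30. The 1-in-17 figure is itself based on completers, but it leaves a wide margin.

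Section 13 also reports the primary proportion with a 95% confidence interval, which uses the actual denominator. That interval still depends on who is counted.

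**Conclusion.** The inconsistency is real and lies in current text: MDS and AML only against all patients, and 33 enrolled including replacements against 33 evaluated. The design is sound (alpha 4.7%, power 81%) if exactly 33 patients of one population are counted.

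The figures of 6.4%, 10.8% and 15.9% at 32, 30 and 28 are conditional. They assume the 60% null, a first stage of 13, the cut-off kept at 16 and omissions unrelated to outcome. A reader might take them as the trial's actual error rate; the documents do not support that. The completer effect pushes further towards passing, by an amount that cannot be sized from the documents.

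Should-fix: the primary analysis set needs to be defined, but the reported early data make a changed decision unlikely.

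**What to change.** State one primary analysis set, in the same words, in the Protocol Summary and Sections 2.1, 3.1, 3.2 and 13:

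- **Set:** the first 33 treated patients. Section 3.2 should say that replacements do not displace anyone from this analysis.
- **Scoring:** patients who stop for toxicity or intolerance before week 12 count as events. Also state how those who leave early for other reasons are scored.
- **Diagnoses:** decide whether the set covers all eligible diagnoses or MDS and AML only, and report the other as supportive. Either is valid if 33 are counted; with MDS and AML only, the set is the first 33 treated patients with those diagnoses.
- **Other counts:** if the number counted is not 33, use a recomputed cut-off: reject at 15 of 32, 14 of 30 or 13 of 28 (alpha 3.6%, 3.8%, 4.1%). State that power falls to about 77–78% at these counts, below the planned 80%. At 31 or 29 it is about 75% or 74%.

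**Cost:** wording in five places and a short cut-off table. Counting all treated patients of any eligible diagnosis needs no extra enrolment for this test. Moving to a lower count costs some power.

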3.0 STUDY DESIGN

This will be a single arm, open label pilot study of weekly dosing of subcutaneous decitabine and venetoclax

Patients will be treated for a minimum of 12 weeks in the absence of clear evidence of progressive disease. Patients who have any response will be permitted to continue treatment until relapse or progression of disease. Primary endpoint will be the percentage of patients who will require dose interruptions due to cytopenias. Secondary endpoints will include assessment of response rates, transfusion dependence, rate of infections and hospitalizations.

Exploratory endpoints will include assessment of the ability of weekly low doses of Dec and Ven to cause DNMT1 depletion on bone marrow samples.

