6.1.1 Decitabine dosing and schedule

Decitabine is given at a dose of 0.1–0.2 mg/kg/day on days 1, 8, 15, 28 (+/- 3 days)..

All patients will receive at least one dose Decitabine every week. If decided by treating physician that the patient needs a more rapid debulking of high disease burden, a second dose can be added. If Decitabine is given twice a week, should preferably be given on two consecutive days.

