6.1.3 Treatment phase

Each treatment cycle is 28 days. Treatment is given weekly and continued without any interruptions

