6.1.4 Dose adjustments for hematologic toxicity

The starting dose of decitabine being administered (0.2 mg/kg) and the dose of venetoclax of 400 mg have been identified by previous pharmacokinetic, pharmacodynamic and clinical studies (administering the drugs singly) as the minimal biologically active doses needed to produce the intended therapeutic molecular pharmacodynamic effect. Based on our experience using this regimen, an anticipated side-effect is neutropenia. However, neutropenia is frequently

caused by the myeloid malignancy being treated. Since doses are already minimal biologically active doses, it is important not to prematurely dose-reduce if neutropenia is from disease and not from therapy:

- To avoid premature dose reduction from already minimal biologically active doses, this protocol incorporates an Induction Phase (week 1-12) during which doses should not be held except for clinically exigent circumstances. After the induction phase, the treating clinical team will need to exercise judgement to distinguish between Grade 4 neutropenia ($ANC < 0.5 \times 10^9/L$) caused by disease *vs* treatment, *aided if necessary with repeat bone marrow aspirate and biopsy*.
- If Grade 4 neutropenia is judged to be from treatment, the first step is to hold treatment until recovery of the ANC to $> 0.5 \times 10^9/L$. If neutropenia recurs, then the next step is to decrease decitabine doses by 25% (0.15 mg/kg).
- If neutropenia recurs even on the reduced dose of decitabine, then decrease dose of decitabine by another 25% (0.1 mg/kg). If neutropenia persists even at this dose and is felt to be from treatment and not from disease, treatment should be held until recovery of the ANC to $> 0.5 \times 10^9/L$. Only continue therapy if it is considered to be in the best interests of the patient. Its at discretion of the treating physician based on clinical benefit to the patient, as to when to go back to the full dose of Decitabine or keep at reduced dose.
- To reduce risks from baseline neutropenia caused by the disease, that may deter or hinder administration of potentially beneficial therapy, this protocol permits concurrent administration of G-CSF (filgrastim or biosimilar $\sim 5 \mu\text{g}/\text{kg}$) if thought to be safe by the treating physician

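### Section 2.1 counts a toxicity delay only beyond two weeks, a threshold absent from the Protocol Summary and Section 13; on a weekly regimen it misses held doses and would undo the 5% error rate of the Simon rule.

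*Combined protocol and SAP*

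**What the plan says.** The primary event is worded in several ways.

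- **Section 2.1:** "defined as delaying or interrupting treatment due to toxicity or intolerability for more than two weeks". It gives no per-episode or cumulative rule, no start for the count and no 12-week window.
- **Protocol Summary, Primary Objective:** "Defined as delaying or interrupting treatment due to toxicity or intolerance during the induction phase (weeks 1-12". There is no minimum duration.
- **Section 3.0:** "Primary endpoint will be the percentage of patients who will require dose interruptions due to cytopenias". There is no minimum duration, and the cause is narrower.
- **Section 13, choice of primary end-point:** the share of patients who can receive "weekly low dose decitabine/ven during the induction period (weeks 1-12) without dose interruptions". There is no minimum duration.
- **Section 13, sample size:** the null (60%) is worded as dose reduction and the alternative (36%) as dose interruption. The stopping rule (7 of 13) and the rejection rule (16 of 33) both count dose reductions.

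Dosing is weekly. Section 6.1.3 says "Treatment is given weekly and continued without any interruptions", and Section 6.1.1 says "All patients will receive at least one dose Decitabine every week". The rationale for cohort expansion (the second section numbered 1.4) reports that among 17 evaluable patients "only one patient had a dose interruption during induction (one dose held", and presents this as early evidence on the primary endpoint.

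**The concern.** Section 13 says the question is whether the regimen can be given continuously. With weekly dosing, one plausible form of intolerance is a short hold of one or two doses, possibly repeated. A threshold of more than two weeks passes over such holds.

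No other planned measure would show the loss. No listed endpoint or analysis measures dose delivered, although Section 6.1.4 says "Since doses are already minimal biologically active doses, it is important not to prematurely dose-reduce". The six-week removal rule in Section 6.3 is not reached by repeated two-week holds.

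The design's error rates are also at stake. Its event rates are set beside a published interruption rate quoted without a duration threshold. If patients are scored with one, the observed rate and the benchmark measure different things, and the stated 5% error no longer describes the decision.

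**Working it through.** **1. The plan's own figures.** Inputs from Section 13: event rates 60% (null) and 36% (alternative, half of 72%); stop at 7 or more events in 13; reject at 16 or more in 33. Let s = 1 − event rate. The regimen is accepted if at least 7 of 13 and at least 18 of 33 patients have no event:

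P(accept) = Σ (x = 7 to 13) C(13,x) s^x (1−s)^(13−x) × P[Bin(20,s) ≥ 18−x]

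- s = 0.40: P(accept) = 0.047; probability of early termination = 0.771.
- s = 0.64: P(accept) = 0.809.

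These match the stated 5%, 0.77 and 80%. A full search returns the same optimal design.

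**2. What the threshold lets through.** There are 12 weekly doses in induction, on nominal days. All 4,096 give/hold patterns were enumerated.

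| Reading | Event needs | Most doses lost without an event |
|---|---|---|
| Per episode, delay from due date | 3 consecutive holds | 8 of 12 (doses on days 1, 22, 43, 64) |
| Per episode, gap since last dose | 2 consecutive holds | 6 of 12 (every second dose given) |
| Cumulative | more than 2 holds in total | 2 of 12 |
| Protocol Summary and Section 13 wording | any hold | 0 of 12 |

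**3. The interim count.** One held weekly dose is a 7-day delay from the due date, a 14-day gap since the last dose, and 7 days in total. None exceeds two weeks. On nominal dosing days every reading of 2.1 scores 0 of 17 where the protocol reports 1 of 17.

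**4. Effect on the decision, illustration.** Assume that each weekly dose is held independently with probability q. This is not from the documents. If 60% of patients have at least one hold, q = 1 − 0.40^(1/12) = 0.0735.

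| Rule | Scored event rate | P(accept) |
|---|---|---|
| Any hold | 60% | 0.047 |
| 2 consecutive holds | 5.5% | > 0.99 |
| More than 2 holds in total | 5.3% | > 0.99 |
| 3 consecutive holds | 0.4% | > 0.99 |

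If 72% have at least one hold (q = 0.1006), the three threshold rules give 9.8%, 11.3% and 0.9%, and acceptance again exceeds 99%. A cumulative limit alone would therefore not restore the error rate.

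**5. Without independence.** Holds may cluster, which would push more patients over the threshold. Let f be the share of patients with a hold who stay under it; the documents give no hold durations, so f is an assumption. The scored rate is 0.60 × (1 − f).

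| f | Scored rate | P(accept) |
|---|---|---|
| 0 | 60% | 0.047 |
| 0.20 | 48% | 0.361 |
| 0.30 | 42% | 0.606 |
| 0.40 | 36% | 0.809 |
| 0.50 | 30% | 0.928 |

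Even if only one such patient in five stays under the threshold, the 4.7% error becomes 36%.

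**The case against.** A reader might infer that the plan lets a patient lose 8 of 12 doses and still count as uninterrupted. The documents do not establish that. Section 2.1 never says per episode, and 8 is the most extreme of its readings. The Protocol Summary and Section 13 have no threshold, and the one scoring on record treated a single held dose as an interruption. This part of the objection stands: what is shown is an undefined and conflicting threshold, not a settled scoring practice.

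The Section 13 rules count dose reductions, so 2.1 events do not feed them as literally worded. That stands too; the effect on the decision is conditional on scoring by 2.1. For the same reason, a reader who combines 4 of 12 doses with a reduction to 0.1 mg/kg, and concludes that about 17% of planned exposure would pass, goes too far. Such a patient has had a dose reduction and is an event under the Section 13 wording.

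Holds are discouraged in induction (Sections 6.1 and 6.1.4) and should be reviewed with the study chairs. Table 1 restarts treatment at a reduced dose after qualifying non-hematologic toxicity, so some repeated holds would surface as reductions. The interim data show one held dose in 17 patients. Frequent unseen holds are thus a possibility, not an observation. None of this removes the conflict between 2.1 and the benchmark, or the freedom to choose a rule after seeing the data.

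**Conclusion.** The point holds in this form: the two-week threshold in Section 2.1 is incompletely defined, contradicts the Protocol Summary and Section 13, does not match the interim count, and does not fit the hypotheses of the design. If it were used for scoring, the 16-of-33 rule would be much easier to pass than the stated one-sided 5% implies. Under the independent-hold illustration, acceptance at the null exceeds 99% for every reading; in the assumption-free-of-independence range it is 36% to 93% for f from 0.20 to 0.50.

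The conflict between sections and the mismatch with the interim count need no modelling beyond nominal dosing days. The size of the error inflation depends on the hold model or on f, neither of which the documents supply. They also do not show whether the trial behind the 72% figure applied a threshold; it is only quoted without one.

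**What to change.** In Section 2.1, delete the two-week clause. Define the event as any scheduled weekly dose of decitabine or venetoclax in weeks 1-12 that is omitted or interrupted because of toxicity or intolerance, or delayed for that reason beyond the dosing window the protocol states. Use this one event in the Protocol Summary and Sections 3.0 and 13, including the hypotheses and the 7-of-13 and 16-of-33 rules that now speak of dose reductions.

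The definition must name the window it uses: Section 6.1.1 gives ±3 days for decitabine, Section 6.1.2 gives ±1 day for venetoclax, and the study calendar has ±4 days for visits. The listed dosing days (day 22 in some places, day 28 in others) must also be reconciled so that a scheduled dose is unambiguous.

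As a descriptive supplement, report relative dose intensity over weeks 1-12 for each drug (dose delivered divided by dose planned).

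The cost is protocol and analysis wording plus actual dosing dates and doses. The interruption rate may be less favourable. The interim patients must be re-scored from dosing dates: the interim report mentions only a held dose and gives no dates or late doses, so it cannot be assumed that 1 of 17 would be unchanged.
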